Aim 1 calls for comparing pre/post session change in exhaled CO, and in urinary levels of cotinine, NNAL, SPMA, and 1-HOP in first morning urine samples the morning of, and the morning after, each of 3 WP smoking sessions at home: (Session 1) using charcoal to heat the tobacco and only water in the jar; (Session 2) using charcoal to heat the tobacco and adding ice cubes in the jar; and (Session 3) using electrically heated tobacco and only water in the jar. Among smokers, differences in pre/post change on CO and each biomarker between sessions 1 & 2, and between sessions 1 & 3, will be assessed by mixed regression models to handle repeated measures on each participant. Demographics, duration of smoking, and possible confounding factors, such as number of smokers inside the home and years smoked, will be included as covariates.

Power analysis. As no data exist on effect sizes of differences between session configurations for Aim 2, in Table 4 we show estimated power to detect difference for a range of potential intra-class correlations (ICC) and an effect size of .40 (medium by Cohen's criteria), based on paired z-test, n=50, two-sided alpha=.05. Estimates are conservative, since addition of covariates and adjustment for pre-session CO or urinary biomarker levels in the analyses will increase power.

Table 4. Power				
estimate	es			
Effect	ICC	Darran		
Size	icc	Power		
0.40	0.25	0.637		
0.40	0.50	0.807		
0.40	0.75	0.979		

Aim 2 will examine levels of urinary Furan-BDA-NAL following the analysis strategy described in Aim 1, but using data only from Session 1, the configuration commonly practiced in naturalistic settings, using charcoal to heat the tobacco, and room temperature water in the jar. We will begin with a comprehensive descriptive analysis of demographics and Furan-BDA-NAL levels and their distribution in WP smoker participants. As in Aim 1, analyses will identify differences in metabolite levels between smokers vs. non-smokers, and between pre vs. post WP smoking Session 1, for the sample overall as well as by demographic categories (age, gender, BMI). Pearson's correlations will be conducted between urinary levels of Furan-BDA-NAL and values of other metabolites (cotinine, NNAL, SPMA, and 1-HOP) quantified for WP smoking Session 1.

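### Table 4 gives power for a paired comparison of two values, while the Aim 1 text contrasts pre/post changes without the pre-session covariate that the power paragraph assumes

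*Combined protocol and SAP*

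**What the plan says.** All the relevant text is under General Statistical Analysis Strategy in the combined protocol and SAP.

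- **Aim 1.** Mixed regression models will assess "differences in pre/post change on CO and each biomarker between sessions 1 & 2", and likewise between sessions 1 and 3. The covariates named are demographics, duration of smoking, and possible confounders, with number of smokers in the home and years smoked as examples. The pre-session level is not named.
- **Power analysis.** Power is shown "for a range of potential intra-class correlations (ICC) and an effect size of .40". The calculation is "based on paired z-test, n=50, two-sided alpha=.05". Table 4 gives .637, .807 and .979 for ICC .25, .50 and .75.
- **Claim about the table.** "Estimates are conservative, since addition of covariates and adjustment for pre-session CO or urinary biomarker levels in the analyses will increase power".
- **Label.** The paragraph opens "As no data exist on effect sizes of differences between session configurations for Aim 2", although the comparison of configurations is Aim 1.

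The plan does not say which SD standardises the .40, or whether the ICC is the correlation of single measurements or of session changes.

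**The concern.** A contrast of changes between sessions 1 and 2 is (post2 - pre2) - (post1 - pre1), which uses four measurements per smoker. A paired test of two single values uses two. If both are scaled by the SD of a single measurement, the four-measurement contrast is noisier and needs more smokers for the same power.

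The power paragraph avoids this by referring to adjustment for pre-session levels, but the Aim 1 text does not carry that adjustment into the model. The two paragraphs therefore describe different analyses. An analyst who follows the Aim 1 text could run a test with materially less power than Table 4 shows, using the same 50 smokers and the same samples. The claim of conservatism would then be wrong for the analysis actually run.

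**Working it through.** **Inputs.** From the power paragraph and Table 4: n = 50, two-sided alpha .05 (critical value 1.96), effect d = .40, ICC = .25, .50, .75. Assumed here, because the plan is silent: d is in single-measurement SDs and, unless stated otherwise, pre and post SDs are equal.

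**Formula.** Power = Phi(d × sqrt(n / v) - 1.96), where v is the variance of the per-smoker contrast in squared SD units. The other tail is negligible.

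**1. Reproduce Table 4.** Take v = 2(1 - ICC), the variance of a difference between two single values.

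| ICC | v | .40 × sqrt(50/v) | Power | Table 4 |
|---|---|---|---|---|
| .25 | 1.5 | 2.309 | .637 | .637 |
| .50 | 1.0 | 2.828 | .807 | .807 |
| .75 | 0.5 | 4.000 | .979 | .979 |

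The match is exact. A paired t-test would give .619, .792 and .975.

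**2. Unadjusted change contrast, equal correlation among all four measurements.** Each change has variance 2(1 - ICC). Changes from different sessions are uncorrelated, because the shared personal level cancels. So v = 4(1 - ICC).

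| ICC | v | .40 × sqrt(50/v) | Power |
|---|---|---|---|
| .25 | 3.0 | 1.633 | .372 |
| .50 | 2.0 | 2.000 | .516 |
| .75 | 1.0 | 2.828 | .807 |

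At ICC .50 the effect detectable with 80% power is (1.96 + .842) × sqrt(2/50) = .56 SD. Because v doubles, about 100 smokers would be needed to regain the Table 4 values.

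**3. Same structure, adjusted for the pre-session level.** Under equal correlation, the between-session difference in pre values is uncorrelated with the difference in post values. Adjustment removes nothing from the post difference, so v = 2(1 - ICC) and power is .637, .807 and .979: equal to Table 4, not above it. A simulation of 50 participants (4,000 runs per ICC) gave .60, .78 and .98 adjusted, against .35, .50 and .80 for raw changes.

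**4. Unequal correlation.** Let w be the pre/post correlation within a session and b the correlation between any two measurements from different sessions. Unadjusted, v = 4(1 - w). Adjusted, v = 2(1 - b) - 2(w - b)²/(1 - b).

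| w | b | Unadjusted v, power | Adjusted v, power | Table 4 at ICC = b |
|---|---|---|---|---|
| .75 | .50 | 1.00, .807 | .75, .904 | .807 |
| .50 | .25 | 2.00, .516 | 1.33, .688 | .637 |

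**5. Smaller pre-session SD.** If the pre-session SD is half the post-session SD, with equal correlation r, the unadjusted v is 2.5(1 - r) in post-session SD units. Power is about .54, .72 and .95.

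**6. Change-score reading.** If .40 is in change-score SDs and the ICC is the correlation between changes, v = 2(1 - ICC) and Table 4 is right for Aim 1. Power is then .516 at a change-score ICC of 0 (v = 2) and .559 at .10 (v = 1.8). Table 4 has no row below .25.

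**The case against.** A reader might infer that Table 4 contains an arithmetic error, or that the study's power really is .37, .52 and .81. The documents support neither.

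- The table's arithmetic is correct, and a paired z-test on two change scores per smoker is a valid test of the Aim 1 contrast. The wording allows the .40 and the ICC to describe change scores.
- It could be replied that change-score ICCs of .25 to .75 are implausible, since a stable personal level cancels from a change. But the plan specifies no random-effects structure. Participants smoke as they usually do, in sessions that usually last 30 to 60 minutes, so heavier inhalers may show larger changes every time. Nothing in the documents fixes that correlation at 0. Nor do they state or justify .25 to .75.
- The power paragraph does mention pre-session adjustment, and the Aim 1 confounders are given as examples rather than a closed list. Adjustment may well be intended.
- Equal correlation among the four measurements is itself an assumption. Pre and post urine samples come from consecutive mornings, while sessions are a week or more apart, so within-session correlation may be higher.
- The plan names no target power and no preferred ICC, so it cannot be said to rely on 80% at the middle row.

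All of this stands, and it limits the low figures to one scenario. It does not remove the mismatch between the two paragraphs, or supply the missing definitions.

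**Conclusion.** The point holds as a mismatch between the Aim 1 text and the power paragraph. With .40 in single-measurement SDs and equal correlation, the two analyses they describe differ at ICC .50 by about .52 (raw change contrast) against .81 (pre-session level adjusted). Over the three ICCs the comparison is .37, .52, .81 against .64, .81, .98.

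The size depends on assumptions that the plan does not settle. The gap disappears if .40 and the ICC are change-score quantities. At between-session correlation .50 it also disappears if within-session correlation is .75.

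The conservatism claim is not assured. Under equal correlation, adjustment only reaches Table 4. It exceeds Table 4 when within-session and between-session correlations differ, which the plan does not state.

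**What to change.** - In the Aim 1 model, analyse the post-session value (log scale where logs are used), with that session's pre-session value on the same scale as a covariate, session as a fixed effect and a participant random intercept.
- State that Table 4 refers to this model, that .40 is in single-measurement SDs, and which measurements the ICC correlates.
- Remove the sentence claiming conservatism, or qualify it with the correlation pattern under which it holds.
- If the unadjusted change contrast is kept, report .37, .52 and .81 beside Table 4 with the assumptions of single-measurement SDs and equal correlation. If change-score units are meant, say so, justify the ICC range and add a row at ICC 0 (.52).
- Correct the Aim 2 label in the power paragraph to Aim 1.

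The cost is wording only. The pre-session values are already collected, and no participants or samples are added. The stated power may look slightly less favourable.

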home in a naturalistic setting: Week 1-Session 1, WP smokers will smoke using 1 quick-light charcoal and room temperature water in the WP jar, Week 2-Session 2, WP smokers will smoke using 1 quick-light charcoal but adding ice cubes to the water in the WP jar, Week 3-Training for session 3, RAs will train participants on how to use a charcoal-free electrically heated WP head to heat the tobacco, and Week 4-Session 3, WP smokers will smoke WP tobacco without charcoal using the electric WP head and room temperature water. We will collect a) Tobacco Use History; b) 4-week Tobacco Use and Exposure Diaries; c) WP Smoking Session Day and Exposure Form; d) CO exposure: Micro+Smokerlyzer® CO monitor will be used for exhaled CO two minutes pre and post each smoking session; and e) 6 first morning urine samples: pre and post the 3 sessions to measure urinary cotinine, NNAL, 1-HOP, and SPMA. We will measure urinary Furan-BDA-NAL in WP smokers who smoke WP tobacco as commonly practiced using quick-light charcoal and room temperature water in the WP jar (urine samples from Session1).

Inclusion Criteria for Participants

Adult waterpipe smoker: A male or female, 18 years or older, who smokes WP tobacco exclusively, smokes at least 1 WP head per month, and smokes at least 1 WP head per WP smoking session, smokes WP at home, agrees to smoke *Starbuzz* WP tobacco, and lives in a 'smoker home'. Adult non-smoker: A male or female, 18 years or older, who lives in a 'non-smoker home'.

Inclusion Criteria for Homes

A Smoker Home: is a home in which residents have smoked WP tobacco exclusively indoors/outdoors at least in the last month. A Non-smoker Home: is a home where to the knowledge of the residents no smokers have lived in and no visitors had smoked indoors/outdoors in the past month, and where a potential nonsmoker participant who has not been exposed to any secondhand smoke at least in the last month resided full-time.

Exclusion Criteria

Adults with major physical/psychiatric illnesses that are judged by the research assistants (RAs) to interfere with ability to give informed consent or to successfully complete an interview will not be included in the study. Daily WP smokers will be excluded because they may not be able to adhere to the wash-out periods before the 3 WP sessions. Pregnant women are also excluded.

Screening Potential Participants

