face using the Tobacco Use History Questionnaire; explain how to complete the diaries on a daily basis; explain the urine collection protocol (2 first morning urine samples/smoking session); provide each participant with 2 coded empty urine cups (no names on urine cups and forms), gloves, 2 zip-lock bags/urine cup; ask participants to store the double sealed urine samples once obtained in his/her personal refrigerator (freezer section) until pickup by RAs the next day. Arrange for the smoking session and home visit on day 7 of the first week study period. The PI and SC will accompany the RAs to their first two homes (more if needed) for hands-on training for data collection. Wash-out period: smokers will abstain from smoking and exposure to any tobacco smoke for 7 days prior to each smoking session. WP smokers will choose a WP smoking day to start the 4-week study period; the RAs will coordinate the Office Visit accordingly. Non-smokers will choose any day to provide 2 first urine samples on two consecutive days. Saliva Test: Trained by the PI, the RAs will use NicAlert to validate non-smoking status, and as a bogus pipeline technique, which we used successfully in our previous studies. NicAlert, a commercial semi-quantitative instant saliva cotinine test, is accurate and valid with high sensitivity (93-100%) and specificity (95-96%) Non-smoking participants will be informed about the purpose of the NicAlert test during the informed consent process. (Appendix K. Saliva Test Procedure) Days 2 - 6: The RAs will contact participants by phone on the 4th day to confirm adherence to the 7-wash-out period and diaries, and on the 6th day to remind participants to collect the first morning urine sample on day 7, and to arrange for a home visit for the first WP smoking session. Day 7: Waterpipe smoking session 1. WP smokers will provide one first morning urine sample and store it in their refrigerator (freezer section). Participants from our previous WP studies stored their urine samples, double bagged in their refrigerator. WP smokers will smoke WP tobacco (10 grams) as they normally do using charcoal and room temperature water in the water jar. The RAs will collect expired CO levels 2 minutes before and 2 minutes after concluding smoking. Day 8: Participants will provide a first morning urine sample. The RAs will pick up the 2 urine samples (frozen), place them in a cooler (to transfer them to our research center laboratory for aliquoting and storage in a freezer at -20°C to be sent out for analyses); pick up the diaries and Waterpipe Smoking Session Day and Exposure From, arrange for the 2nd WP smoking session home visit, provide forms, urine cups package for week 2 of the study.

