
Waterpipe Smoking Session 2. The 7-Day study activities: Days 1 through 7 are similar to session 1 with the exception that the RAs will add one tray of ice cubes and water in the WP jar. The RAs will arrange for a training session to use the charcoal-free electrically heated WP head.

Waterpipe Smoking Session 3. The 7-Day study activities: *Training for session 3.* Any day during the third week, the RAs will arrange to visit the participants to train them on the charcoal-free electrically heated WP head, and arrange for the 3rd smoking session using the electric head. *Smoking session 3*. Days 1 through 7 are similar to session 1 using room temperature water in the WP jar, however using the charcoal-free electrically heated WP head instead of using charcoal. During the last visit, the day after the 3rd smoking session, the RAs will interview participants to complete the *Illnesses and Health Care History Form* (completed during the last day of the study period to avoid biasing smoking behavior), pick up the final urine samples, thank the participants and inform them that they will receive a check from SDSU in the amount of \$250 by mail.

Standardized Setting of the Waterpipe Device, Smoking Protocol, Waterpipe Tobacco and Charcoal

To reduce variance of factors extraneous to our configurations of WP smoking practices, we will standardize setting the WP device, aluminum foil, and amount, type and brand of WP tobacco and quick-light charcoal. We will determine and standardize the volume and commercial brand of drinking water to be placed in the WP jar, and volume of water and added ice cubes to be standardized.

Waterpipe Device. We will purchase 10 new unused WPs similar in specification to the Battelle Research-grade WP: 2L glass water jar, 28.6 cm length of body. All WPs will be the same size, style, and brand. In the kitchen of the participants, before and after each use, the RAs will thoroughly clean the stem and glass jar with soap and water between sessions and between participants. Three new hoses will be used for each smoker.

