Waterpipe Tobacco Protocol and Brand - Starbuzz: All smokers will smoke the WP brand Starbuzz during the 3 WP sessions. We will purchase for each participant one package of Starbuzz tobacco to be used for the 3 smoking sessions and the training session. Following opening the package for session 1, the RAs will place the package in a sealed Ziploc bag and ask the participant to store it in a cabinet at room temperature and away from any direct sunlight until use the following smoking session. The majority of WP smokers use flavored WP tobacco Maassel (Table 2). We identified Starbuzz, a flavored WP tobacco brand, that is manufactured in the U.S. and is popular and accessible to WP smoker consumers based on: (1) a search of 'online vendors' such as hookah-shisha.com, hookahwholesalers.com, thehookah.com, and Amazon.com who provide a customer review section for WP tobacco products; (2) a survey of point-of-sale display of the most frequent WP tobacco brands in 6 Middle Eastern markets and smoke shops that sell WP tobacco in the San Diego area; (3) our preliminary unpublished WP data; and (4) brands most served at 5 WP lounges. We will use a popular flavor 'Double Apple' for all WP smoking sessions as reported in the literature and by our unpublished data (Appendix L. Preferred WP tobacco Flavors & Brands – unpublished data).

Waterpipe Charcoal Protocol and brand - Three Kings quick-light charcoal (40mm): Quick-light charcoal is manufactured to light fast and has been used in previously published studies in naturalistic and laboratroy settings. A standardized protocol will be used in lighting and placing the charcoal on the tobacco-covered head. Three Kings quick-light charcoal (Holland) is an internationally recognized brand, and customarily sold where WP tobacco is sold in Smoke shops and Middle Eastern markets in the U.S. and online. Smokers use them for convenience, since lighting only requires a match or lighter held to it for a few seconds with only a small flame, and usually stay lit up throughout the smoking session.

Questionnaires, Diaries, Forms will be developed based on our previous WP studies.

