Exhaled Carbon Monoxide (CO) Concentrations. We will measure CO exposure using a Micro+ Smokerlyzer® CO monitor for exhaled CO two minutes before lighting the charcoal and 2 minutes at conclusion of each smoking session. CO is a smoke toxicant that reduces the blood's ability to transport oxygen to various organs, including the brain, and can cause dizziness, headache, syncope and nausea. An acute increase in exhaled CO/COHb, and CO poisoning were demonstrated in WP smokers. Post 50 minutes of smoking, mean expired-air CO concentration increased to 32.9 ± 2.7 ppm in WP smokers, and to 7.4 ± 0.5 ppm when smoked cigarettes.

Urinary Biomarkers of Exposure to Waterpipe Tobacco Smoke. Urinary cotinine, NNAL, SPMA, and 1-HOP, will be determined in WP tobacco smokers to assess comparative risk related to WP tobacco smoking across 3 configurations, as shown in Table 1. We expect that this panel of biomarkers will be higher in smokers who add ice cubes in the WP jar; and SPMA and 1-HOP will be lower in smokers who replace charcoal with charcoal-free electric WP head. We will also assess levels of WP smokers' exposure to furan by quantifying its urinary metabolite Furan-BDA-NAL among WP, in which we expect to find an increase post smoking.

Cotinine will be measured as an index of nicotine consumption in WP smokers using emerging WP smoking practices. On average, 70%-80% of nicotine entering the body is converted into its metabolite, cotinine. Daily use of WP tobacco produced a 24-hour mean (95%CI) urinary cotinine level of 785 ng/ml (578-991ng/ml) equivalent to smoking 10

cigarettes/day. Post smoking WP, mean (95% CI) urinary cotinine increased: 11.8 (7.21-19.2) to 55.3 (33.9-90.1) ng/mg creatinine, N=55.

NNAL will be measured as an important tobacco-specific lung carcinogen. In 55 WP smokers NNAL about doubled (2.1-fold) post WP smoking: 1.32 to 2.84 pg/mg creatinine. Higher urinary mean levels (uncorrected) were found in WP smokers in Syria (N=24) [mean (95% CI), 33.0 pg/ml (21.6-50.6 pg/ml)].

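### Does adjusting for the pre-session level, mentioned only as a gain in power, leave the Aim 1 contrast undefined?

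*Combined protocol and SAP*

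**What the plan says.** The Aim 1 paragraph of the combined protocol and SAP sets the comparison: "Among smokers, differences in pre/post change on CO and each biomarker between sessions 1 & 2, and between sessions 1 & 3", to be assessed by mixed regression models for repeated measures. The covariates it lists are demographics, duration of smoking and possible confounders. The pre-session level is not among them.

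The power paragraph that follows shows Table 4 (paired z-test, n = 50, effect size 0.40, ICC 0.25, 0.50 and 0.75) and closes with: "Estimates are conservative, since addition of covariates and adjustment for pre-session CO or urinary biomarker levels in the analyses will increase power". This is the only mention of pre-session adjustment. The paragraph labels the comparison Aim 2, although it describes Aim 1.

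The order of configurations is fixed in Study Design and Target Population, from "Week 1-Session 1, WP smokers will smoke using 1 quick-light charcoal and room temperature water in the WP jar" to "Week 4-Session 3, WP smokers will smoke WP tobacco without charcoal using the electric WP head and room temperature water". Under Waterpipe Smoking Session 1, "smokers will abstain from smoking and exposure to any tobacco smoke for 7 days prior to each smoking session". Before session 3 there is also a training visit: "Any day during the third week, the RAs will arrange to visit the participants to train them on the charcoal-free electrically heated WP head". The tobacco package is "to be used for the 3 smoking sessions and the training session".

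**The concern.** A change score and a baseline-adjusted score estimate the same quantity when mean baselines are equal. Randomised or counterbalanced order would give that on average. Here each configuration belongs to one week, and the lead-in differs:

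- Session 1 follows the smoker's own use before washout.
- Session 2 follows session 1 by about 7 days.
- Session 3 follows session 2 by about 14 days, with a training visit in between for which tobacco is provided.

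If mean pre-session levels drift between sessions, the two analyses can give different answers on the same data. One could be null and the other significant. The plan cites adjustment only for its power and does not say whether it replaces or supplements the change contrast. The question touches CO and four biomarkers in two comparisons each, so 5 × 2 = 10 contrasts. The stake would be a choice of analysis made after the results are seen.

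**Working it through.** **1. The plan's own figure.** Power = Φ(0.40·√50 / √(2(1 − ICC)) − 1.96).

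- ICC 0.25: Φ(2.309 − 1.96) = 0.637
- ICC 0.50: Φ(2.828 − 1.96) = 0.807
- ICC 0.75: Φ(4.000 − 1.96) = 0.979

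All three match Table 4. The formula takes one value per session, so it fits change scores if the 0.40 and the ICC describe change scores. If they describe single levels with exchangeable correlation, the variance of a difference in change is 4(1 − ICC)/50 and power is 0.372, 0.516 and 0.807. The document does not state the scale.

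**2. How far apart the two contrasts are.**

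- Change: (post_k − post_1) − (pre_k − pre_1)
- Adjusted: (post_k − post_1) − b(pre_k − pre_1)
- Size of the gap: (1 − b)·d, where d is the shift in mean pre-session level

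No d is given, so it has to be assumed. At d = 0.2 SD the gap is 0.20, 0.15, 0.10, 0.05 and 0 SD for b = 0, 0.25, 0.5, 0.75 and 1. At d = 0 it is zero for every b.

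For scale, the log SD is ln(upper/lower)/3.92 × √N. The cotinine paragraph reports that "urinary cotinine increased: 11.8 (7.21-19.2) to 55.3 (33.9-90.1) ng/mg creatinine, N=55". The pre-session log SD is then ln(19.2/7.21)/3.92 × √55 = 1.85, and 0.2 SD is a factor of exp(0.2 × 1.85) = 1.45. The SPMA paragraph (0.17 to 0.41, N = 50) gives 1.59 and a factor of 1.37.

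**3. Which contrast is less biased.** Let a share p of the shift carry into the post sample. The bias is (p − 1)d for change and (p − b)d for adjustment. Adjustment is the less biased when p < (1 + b)/2.

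Take n = 50, ICC 0.50, d = 0.2 and no configuration effect. Let f be the share of within-person variance common to a session's pre and post samples, with b = f. Contrast variances are 4(1 − ICC)(1 − f)/50 for change and 2(1 − ICC)(1 − f²)/50 for within-participant adjustment. Two-sided rejection rates at f = 0/0.3/0.5/0.6:

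| Shift | Change | Adjusted |
|---|---|---|
| Persists fully (p = 1) | 5/5/5/5% | 29/18/13/11% |
| Pre sample only (p = 0) | 17/22/29/35% | 5/7/13/19% |

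For example, adjusted with p = 1 and f = 0: SE = √0.02 = 0.141, 0.20/0.141 = 1.414, rejection 29%. The table shows that neither analysis dominates. It is not evidence of size, because d, p and f are all assumed and pre and post variances are set equal. The SPMA intervals do not support that last assumption: (1.588/1.317)² = 1.45.

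**4. What p might be.** Suppose residual exposure from earlier smoking simply adds to the post-session level without decline.

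- Cotinine: a 1.45-fold shift on 11.8 adds 5.3, so post moves from 55.3 to 60.6 and p = ln(60.6/55.3)/ln(1.45) ≈ 0.25.
- SPMA: a 1.37-fold shift on 0.26 adds 0.096, so post moves from 0.58 to 0.676 and p = ln(0.676/0.58)/ln(1.37) ≈ 0.49.

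Both fall below (1 + b)/2, which is at least 0.5 for any b ≥ 0. Under residual carry-over, then, unadjusted log change would be the more biased of the two. Insisting on it would not make the result safer.

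**5. With no shift.** Both contrasts are unbiased, and the adjusted variance relative to change is (1 + f)/2. That is lower by 50/35/25/20% at f = 0/0.3/0.5/0.6. The adjusted variance is also never above the 2(1 − ICC)/50 used in Table 4, which is the sense in which the plan calls its estimates conservative.

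**The case for a change.** The strongest case for a change is that the plan names one contrast and then commits the analyses to another. It gives no model equation, and General Statistical Analysis Strategy leaves the analyses to be determined by the study team. Naming a primary contrast would cost a sentence and one extra model on data already collected.

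Much of this stands. The two contrasts do differ under a shift, the fixed order does not rule one out, and how the pre-session level enters the model is not written down.

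It does not amount to a defect, for these reasons:

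- Aim 1 states its contrast twice, as change. A mixed model with a session-by-time term on pre and post values estimates exactly that, and it is a natural reading of the text. The remark on adjustment supports the power estimate and does not restate the aim.
- The design addresses unequal pre-session levels directly. It has a washout before every session, daily diaries, a day-4 adherence call and exclusion of daily smokers.
- The proposed remedy would let the sponsor choose either contrast, since neither is safe throughout.
- Treating disagreement between the two as a warning would misfire. With no shift, a true effect of 0.40, ICC 0.50 and b = 0, simulated power was 0.50 for change and 0.78 for adjustment. At least 28% of trials would then disagree on significance through precision alone.
- Neither contrast removes order or period effects, so naming one would not mend the fixed order.

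**Conclusion.** No change to the plan follows. The gap between the contrasts is (1 − b)·d. It is zero if pre-session levels are equal across sessions, and at most 0.20 SD for an assumed 0.2 SD shift with b between 0 and 1. The documents give no basis for d, so the actual size cannot be computed, and the 7-day washout may make it negligible.

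What is left is detail that analysts fill in when they write the mixed model (outcome, session term, form of the pre-session term), plus the scale of the 0.40 and the ICC and a clerical slip in the aim number. The descriptive levels by configuration already planned in General Statistical Analysis Strategy should largely show any drift in pre-session levels.

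The conclusion rests on reading Aim 1 as written, with change as its contrast, and on adherence to the washout. A marked drift in pre-session levels would call for caution in interpreting either contrast.
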